## Procedures for discontinuation

Subjects who discontinue should always be asked about the reason(s) for their discontinuation and the presence of any AEs or ADEs. If possible, they should be seen and assessed by an investigator(s). Ongoing AEs and ADEs should be followed up.

A subject will be classified as lost to follow up only if, he/she has failed to return to the required study visits and his/her dental status remains unknown, despite multiple attempts to contact the subject via telephone, fax, email, certified letter and through subject locator agencies (if allowed per national regulation).

### Procedures for handling incorrect enrolled subjects

Subjects not meeting the inclusion/exclusion criteria for a study should, under no circumstances, be enrolled into the study - there can be no exceptions to this rule. When subjects not meeting the study criteria are enrolled in error, or if subjects subsequently fail to meet the criteria for the study after enrollment, they will be excluded from the study and from the analyses.

If subjects are excluded intraoperatively (e.g. dehiscence), the subjects will receive a standard grafting treatment at no cost. However, an implant placement at the site will be at the patient's cost.

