# 3 STUDY PLAN AND PROCEDURES

# 3.1 Overall study design and flow chart

The study is designed as a randomized control prospective study with two study centers.

The study population will consist of individuals requiring ridge preservation prior to dental implant therapy in a single tooth extraction socket in premolars and molars except for third molars.

A total of 44 subjects will be randomized to obtain at least 40 evaluable subjects in anticipation of a 10% dropout rate. 44 evaluable subjects will be enrolled at two centers. Each subject will be randomized into one of two groups: group A (GUIDOR® easy-graft CLASSIC) and group B (FDBA and collagen plug). Each center will enroll 22 evaluable subjects, 11 per group ideally.

The ridge preservation study will be a 5-month follow-up with 9 main clinic visits to reentry/implant placement. Three additional clinic visits for the observation period will be scheduled after crown delivery to the study site.

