## Surgical Procedure

After administration of local anesthesia, the tooth will be extracted without raising a mucoperiosteal flap. A minimally invasive extraction procedure helps protection and preservation of the surrounding socket bone. Horizontal bucco-lingual ridge width at crest will be measured intraoperatively and recorded in CRF. The bucco-lingual width will be measured intraoperatively using a pointy caliper. The width will be measured 1mm apical to the alveolar crest level.

If fenestration and/or dehiscence are present when the marginal bone is sounded by a perioodontal probe through the sulcus around the tooth or fracture of the buccal bone is noted upon extraction, the subject will be excluded from the study and treated as a normal patient of the clinic (Incorrect enrollment).

After thorough debridement of granulated tissue and rinsing with sterile saline the prepared easy-graft® CLASSIC (Group A) or FDBA (Group B) will be grafted to the socket defect. Easy-graft CLASSIC should be prepared according to manufacturer's instruction. FDBA will be rehydrated by sterile saline before grafting. The graft materials will be condensed to achieve a fill of the socket to level of crestal bone.

VERSION 1.1 10(33)

A bioabsorbable collagen wound dressing (Collagen Plug, Zimmer Dental Inc.) will be placed on the top of the graft (FDBA) and secured with sutures. (Group B).

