## 3.2.5 Discontinuation of subjects from treatment or assessment

## Criteria for discontinuation

Subjects may be discontinued from study treatment and assessments at any time. Specific reasons for discontinuing a subject from this study are:

- Voluntary discontinuation by the subject who is at any time free to discontinue his/her participation in the study, without prejudice to further treatment
- Safety reasons as judged by the investigator and/or Sponsor

VERSION 1.1 17(33)

- Severe non-compliance to protocol as judged by the investigator and/or Sponsor
- Incorrect enrolment (i.e., the subject does not meet the required inclusion/exclusion criteria for the study)
  - If a dehiscence and/or a fenestration are observed intraoperatively upon tooth extraction, the subject will be excluded.
- Subject received further dental therapy on study site or adjacent teeth without consent of investigator (e.g. new crown, periodontal surgery, or orthodontics on adjacent teeth)
- Subject lost to follow-up

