# 3.4 Method of assigning subjects to treatment groups

Screening numbers will be assigned at day of screening (Visit 1). Subjects at center 1 will receive numbers starting at S101 and subjects at center 2 will receive numbers starting at S201. Subject numbers (subject ID) will be consecutively allocated in series at day of inclusion (Visit 2). Subjects at center 1 will receive numbers starting

VERSION 1.1 19(33)

at 101 and subjects at center 2 will receive numbers starting at 201. Enrollment will continue until 22 subjects at each center have been allocated a subject ID. If a subject discontinues, the subject number will not be reused.

Subjects will be randomized strictly sequentially at enrollment (Visit 2). The randomization schedule will be generated using a validated system under the responsibility of the data management team. The randomization procedure will be concealed. Randomization will be stratified by center and smoking habit, i.e. each center will have 11 subjects in each group A and B, respectively with an equal number of subjects with current tobacco consumption per group. The allocation will be revealed to the clinician only following tooth extraction for ridge preservation.

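### Section 3.2.5 removes later criterion failures from the analyses with no cut-off, while no analysis set is defined; separately, Sections 3.1 and 3.4 conflict on whether exclusions at extraction use up randomised places.

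*Combined protocol and SAP*

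**What the plan says.** **Removal from the analyses.** Section 3.2.5 (Procedures for handling incorrect enrolled subjects) covers subjects enrolled in error, and adds that "if subjects subsequently fail to meet the criteria for the study after enrollment, they will be excluded from the study and from the analyses". No time point, decision-maker or masking is stated. The only example, in the next paragraph, is a finding made during surgery.

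**Analysis set and timing.** Section 6 names no analysis set, and Section 3.1 uses the term evaluable without defining it. Section 6.1 makes a SAP optional and asks only that it precede database lock. Section 5.1 describes one lock, at the end of the study. The Synopsis (Study design) opens the randomisation key earlier, once all re-entry visits are complete, for the primary analysis.

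**Randomisation and exclusion at extraction.** Section 3.4 issues the subject ID and randomises at Visit 2. It then says "Enrollment will continue until 22 subjects at each center have been allocated a subject ID", and IDs are not reused. It also says "The allocation will be revealed to the clinician only following tooth extraction for ridge preservation". Extraction is at Visit 3. There, under Surgical Procedure in Section 3.1.3, if "fracture of the buccal bone is noted upon extraction, the subject will be excluded from the study". Section 3.2.5 (Criteria for discontinuation) adds: "If a dehiscence and/or a fenestration are observed intraoperatively upon tooth extraction, the subject will be excluded". Section 6.1.3 does not replace dropouts.

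**Numbers.** Section 3.1 says "A total of 44 subjects will be randomized to obtain at least 40 evaluable subjects in anticipation of a 10% dropout rate", and then "44 evaluable subjects will be enrolled at two centers", with 22 evaluable subjects at each centre.

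**The concern.** Removing randomised subjects from the comparison is least harmful when the decision cannot depend on the arm. Section 3.2.5 does not secure this. Under Section 3.2.3, heavier smoking, a medication that affects healing, or a local condition that compromises healing are exclusion criteria, and each can first arise after the graft is placed. The treating clinician then knows the graft. A local healing problem may also be related both to the material and to the bone change being measured.

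A predefined analysis set would normally settle who is counted. Here there is none, and a SAP written within the stated deadline could still follow the opening of the key. Membership of the primary comparison therefore stays open after the allocation is known.

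The second matter is loss of numbers. If the 22 IDs per centre are issued before the socket is inspected, a subject excluded at extraction has already taken one of the 44 places.

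**Working it through.** **1. The plan's own sample size.** Inputs (Sections 6.1 and 6.3): difference 0.7 mm, SD 0.8, two-sided alpha 0.05, power 80%. Normal approximation per group: 2 × (1.960 + 0.842)² × 0.8² / 0.7² = 20.5, so 21. The stated 20 is reproduced closely if read per group, which the 40 evaluable in Section 3.1 implies. The dropout allowance is 20 × 1.1 = 22 per group. Expected evaluable after 10% dropout is 44 × 0.9 = 39.6, so no reserve is left for exclusions at extraction if they come on top of dropout.

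**2. Effect of late removals on type I error.** Assumptions: no true effect, 20 per group, two-sided Wilcoxon test, all removals from one arm, taking the k subjects lowest on a score that has correlation rho with the outcome. Simulation, 80,000 replicates; with no removal the rate is 5.0%.

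| Removed (k) | rho 0.3 | rho 0.5 | rho 1.0 (exactly the worst outcomes) |
|---|---|---|---|
| 1 | 5.0%, 0.024 mm | 5.0%, 0.041 mm | 6.1%, 0.079 mm |
| 2 | 5.1%, 0.045 mm | 5.8%, 0.072 mm | 8.9%, 0.146 mm |
| 3 | 5.5%, 0.063 mm | 6.8%, 0.104 mm | 13.0%, 0.208 mm |

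Each cell gives the type I error and the shift in that arm's mean. The last column is an upper bound for that many one-arm removals, not an expectation.

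**3. Effect of exclusions at extraction on numbers.** The documents give no exclusion rate f, so 1 to 5% is assumed, on top of 10% dropout.
- Expected evaluable = 44 × 0.9 × (1 − f).
- Chance of at least 40 = upper tail of Binomial(44, 0.9 × (1 − f)).
- Power = simulated Wilcoxon test (0.7 mm, SD 0.8, normal data), with each arm's size drawn from Binomial(22, 0.9 × (1 − f)).
- Extra enrolled to reach 44 assignments = 44/(1 − f) − 44.

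| f | Evaluable | Chance of at least 40 | Power | Extra enrolled |
|---|---|---|---|---|
| 0 | 39.6 | 55% | 73.7% | 0 |
| 1% | 39.2 | 47% | 73.2% | 0.4 |
| 2% | 38.8 | 40% | 72.8% | 0.9 |
| 3% | 38.4 | 33% | 72.3% | 1.4 |
| 5% | 37.6 | 22% | 71.2% | 2.3 |

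The power loss is 73.7 − 73.2 = 0.5 points at 1%, and 73.7 − 71.2 = 2.5 points at 5%.

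**4. Sensitivity to the dropout assumption.** Section 6.3 does not tie the 10% to a time point, and the primary endpoint is at month 4. If only 5% are lost by Visit 8 (assumed), 44 × 0.95 = 41.8 are expected, with a 93% chance of at least 40. Adding 2% exclusions gives 44 × 0.95 × 0.98 = 41.0, with an 82% chance, against 40% when the full 10% is applied.

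**The case against.** **The late-removal rule may be narrower than it reads.** It stands under a heading about incorrect enrolment, and its example is intraoperative. The CBCT examiners are masked. Breaches of on-study restrictions could instead be treated as severe non-compliance, which discontinues the subject but says nothing of the analyses. This limits the likely harm, but the sentence itself is open-ended, the criteria it refers to include smoking, medication and local conditions, and the masked examiners are not given the exclusion decision.

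**Exclusions at extraction.** A reader might infer that these also bias the comparison. The documents do not support that: the allocation is withheld until after extraction, so these decisions are probably masked. What is missing is a requirement that the socket check be recorded before the reveal.

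**The lost places depend on a reading.** Early randomisation alone loses nothing; the loss comes from combining it with a cap that counts IDs. The 22 evaluable per centre in Section 3.1 can be read as enrolling past incorrect enrolments, and Section 6.1.3 bars replacing dropouts, which need not include them. This stands, so the defect is a conflict between Sections 3.1 and 3.4. Counting only subjects who pass extraction towards the cap would also avoid the loss.

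**Size.** A reader might suppose 10 to 20% exclusions and a large fall in power. Nothing in the documents supports such rates, since CBCT must already show an intact ridge without dehiscence or fenestration.

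**Visit 9.** A reader might infer that subjects terminated for insufficient ridge width (Section 3.1.9) lose their Visit 8 data. That section ends their participation but, unlike Section 3.2.5, does not mention the analyses. The point needs only a clarifying sentence.

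**Conclusion.** The main point holds. The plan directs removal from the analyses for criterion failures that may arise after the graft is known, with no cut-off, no masked decision and no analysis set fixed before the key is opened. The rule permits arm-dependent removals; it does not call for them, and a conclusion that the comparison will be materially biased would go too far. Under the assumed correlations of 0.3 to 0.5, type I error stays at about 5 to 7% for 1 to 3 one-arm removals. The 9 to 13% for 2 or 3 removals is an upper bound under one-arm removal.

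The secondary point holds as an inconsistency of uncertain cost. Under the Section 3.4 cap, each exclusion at extraction uses up a randomised place. The power loss is about 0.5 to 2.5 points at an assumed 1 to 5% exclusion rate. Nothing is lost against the target of 40 if exclusions plus dropouts by Visit 8 total 4 or fewer. Removing this loss would restore only the dropout-alone position of about 74% power; the remaining gap to 80% has other causes.

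Both should be fixed because the remedy is mostly wording.

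**What to change.** - **Section 3.2.5:** limit exclusion from the analyses to criterion failures documented before the allocation is revealed.
- **Section 6:** define the primary analysis set as all randomised and grafted subjects with a baseline and a Visit 8 CBCT, in their allocated group. State that Visit 8 data of subjects terminated at Visit 9 for ridge width are kept.
- **Later breaches:** list them as protocol deviations by arm. Handle them only in a sensitivity analysis whose membership a masked reviewer fixes before the key is opened, not merely before database lock.
- **Section 3.1:** state 44 randomised and at least 40 evaluable, and remove the figures of 44 evaluable and 22 evaluable per centre.
- **Section 3.4:** assign the concealed randomisation number after extraction and documented confirmation of an intact socket, before the reveal, and count 22 per centre from those assignments.

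**Cost.** No extra visits or procedures are needed; Section 3.1.3 already allows enrolment and surgery on the same day. Reaching 44 assignments takes about 0.4 to 2.3 more enrolled subjects at 1 to 5% exclusions. Each subject excluded during surgery receives the no-cost standard grafting that Section 3.2.5 already provides. The concealed assignment must be available at surgery, and the amendment must be notified to or approved by each IRB (Section 7.4).

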### 3.3 Treatments

## 3.3.1 Identity of investigational product and comparators

GUIDOR® easy-graft CLASSIC is bone grafting system contains: syringe containing beta-tricalcium phosphate (β-TCP) granules coated with poly (lactide-co-glycolide) (PLGA) and ampule containing BioLinker™ Activator (N-methyl-2-pyrrolidone and water).

Easy-graft CLASSIC is a bioresorbable, synthetic, porous bone graft substitute. It consists of two components: granules (supplied in syringe) and BioLinker activator (supplied in ampule). After mixing the components together, easy-graft CLASSIC forms a moldable mass that can be applied directly from the syringe into the bone defect. easy-graft CLASSIC hardens in contact with body fluids, allowing a working time of approximately one minute after application into the bone defect. Easy-graft CLASSIC is provided in the particle size of  $500-1000~\mu m$ . Easy-graft CLASSIC is a biocompatible and osteoconductive material that allows for complete resorption by

VERSION 1.1 18(33)

the body. β-TCP and PLGA are derived from synthetic raw materials. Easy-graft CLASSIC comes sterilized via gamma irradiation.

Collagen Plug, Zimmer Dental Inc. is made from type I bovine collagen. Collagen Plug is a biocompatible, sterile resorbable highly porous collagen wound dressing for bleeding control, stabilizing the blood clot, and protecting the wound bed. Its dimensions are 10mm X 20 mm and have a resorption period of 10-14 days.

Lifenet Health® mineralized cortical freeze-dried particulate bone allograft (FDBA) has a particle size of 250-1000  $\mu m$ . It is sterilized via Allowash XG® technology, consisting of rigorous screening and assessment of donor tissues; cleaning with hypotonic solutions and antimicrobial reagents; decontamination, disinfection, and cleaning regimens with hydrogen peroxide and isopropanol alcohol solutions; and terminal sterilization with gamma irradiation. The particulate material comes packaged in a sterile vial in a blister pack.

## 3.3.2 Labeling

All grafting materials will be labelled as follows:

- "Reference number"
- "Lot number"
- "Expiration date"

All dental implant materials will be labeled as follows:

- "Reference number"
- "Lot number"
- "Expiration date"
- "Single use"
- "Sterile"

The reference number and lot numbers will be recorded in clinical records (source data) and CRF.

## 3.3.3 Storage

All investigational products must be kept in a secure place under appropriate storage conditions. Descriptions of the appropriate storage and shipment conditions are specified on the study product label and product information.

# 3.3.4 Accountability

Distributed study products will be used for this study in accordance with the study protocol. All product deliveries, distributions and dispositions will be confirmed by the investigator or delegate, and recorded in the log.

# 3.4 Method of assigning subjects to treatment groups

Screening numbers will be assigned at day of screening (Visit 1). Subjects at center 1 will receive numbers starting at S101 and subjects at center 2 will receive numbers starting at S201. Subject numbers (subject ID) will be consecutively allocated in series at day of inclusion (Visit 2). Subjects at center 1 will receive numbers starting

VERSION 1.1 19(33)

at 101 and subjects at center 2 will receive numbers starting at 201. Enrollment will continue until 22 subjects at each center have been allocated a subject ID. If a subject discontinues, the subject number will not be reused.

Subjects will be randomized strictly sequentially at enrollment (Visit 2). The randomization schedule will be generated using a validated system under the responsibility of the data management team. The randomization procedure will be concealed. Randomization will be stratified by center and smoking habit, i.e. each center will have 11 subjects in each group A and B, respectively with an equal number of subjects with current tobacco consumption per group. The allocation will be revealed to the clinician only following tooth extraction for ridge preservation.

# 3.5 Pre-study, concomitant and post-study treatment(s)

Systemic corticosteroids or any other medication that would compromise postoperative healing and/or bone healing are not allowed.

After surgery, mouth rinsing with 0.12% non-alcohol chlorhexidine rinse will be subscribed according to local routines.

Subjects will be given post-surgical instructions with regards to diet and oral hygiene. Oral hygiene instructions will be given to the subjects at all study visits.

Other medication, which is considered necessary for the subject's safety and well-being, may be given at the discretion of the investigator(s). The administration of all medication must be recorded in the appropriate sections of the CRF. This includes all mediation administered pre-surgical, during surgery and post-surgical.

VERSION 1.1 20(33)

# 4 MEASUREMENTS OF STUDY VARIABLES AND DEFINITIONS OF OUTCOME VARIABLES

# 4.1 Screening and demographic measurements

The following data will be recorded via a standard CRF:

- Date of birth
- Sex
- Race
- Relevant medical and surgical history
- Medication
- Oral examination
- Local condition of alveolus and adjacent teeth
  - Periodontal disease
  - o Bone loss
  - Caries
  - Endodontic treatment
  - Existing periapical radiolucency
- Tobacco use
- Reason for tooth extraction
- Previous bone graft, soft tissue graft, or apical surgery
- Opposing tooth contact in maximum intercuspation

# 4.2 Efficacy

# 4.2.1 Primary outcome variable

## 4.2.1.1 Dimensional osseous changes

The amount of horizontal and vertical bone changes will be calculated using data from DICOM images acquired by CBCT using 3D software.

#### 4.2.1.1.1 Methods of assessment

CBCT scans will be obtained at baseline and 4 months following ridge preservation (Visit 8). Linear measurements will be done at the University of Iowa by a single, calibrated examiner. Volumetric assessments will be performed by an external reading center in Georgia that is associated with the University of Iowa. All examiners will be masked for the therapy applied in each case.

For the horizontal and vertical measurements a plane of reference will be set to allow for reproducible and reliable assessments (in mm) between both baseline and 4-month datasets.

Volumetric assessments will be performed using a specific software (Simplant 16 Pro) via selection of a region of interest (ROI) that includes only hard tissues. The same segmentation settings of the ROI selected in the baseline scan will be transferred to the 4-month reconstruction in order to generate comparable volumes. Volume

VERSION 1.1 21(33)

measurements will be expressed in cc, which allows for a calculation of the % of volumetric reduction that took place from baseline until one month prior to surgical re-entry.

#### 4.2.1.1.2 Derivation or calculation of variable

The mid-alveolar point positioned on a tangent drawn from the mesial and distal adjacent tooth CEJs will be used as a reference point for assessment of dimensional bone changes in the Z-axis (bone width) and Y-axis (bone height). The changes in the bone dimensions between baseline (Visit 2) and 4 months (Visit 8) will be measured. The change for each study site will be compared longitudinally and the average for each treatment group will be calculated and compared among treatment groups.

## 4.2.2 Secondary outcome variables

## 4.2.2.1 Qualitative histological evaluation

A core of bone from the defect sites will be harvested for qualitative histological assessment.

#### 4.2.2.1.1 Methods of assessment

Trephined bone cores will be obtained from a subset of patients from each treatment group (Visit 9). Tissues stored in 10% neutral buffered formalin (NBF) will be fixed for at least 7 days. All bone core samples will be sent to University of Maryland. The samples will be subsequently rinsed in phosphate buffered solution (PBS) and demineralized by immersion in ethylenediaminetetraacetic acid (EDTA) for a minimum of 5 weeks. Cores will be embedded in paraffin, sectioned along a transverse plane, and stained with conventional hematoxylin and eosin (H&E) technique, and coverslipped for qualitative histologic analysis.

Images of sections will be taken with microscope and connected with digital camera. Quantitative assessment of newly formed bone and, residual bone graft particles and non-mineralized tissue on histological section with H&E staining will be performed at least 5 images randomly chosen in the same section and analyzed with recommended software. The assessment will be performed by the central reader at University of Maryland.

